# 7.2.3. Preparation of Plasma Biomarker and PK Samples from PET Sub-study Participants

At each blood collection for biomarkers and PK, blood samples will be drawn into two Vacutainer® tubes (10 mL per tube) containing K2EDTA. The tubes will be placed immediately on ice upon collection. Following the instructions within the Laboratory Manual, the plasma samples will be centrifuged, frozen (within 30 minutes of centrifuging), and shipped to the central laboratory.

# 7.2.4. CSF Assays

Approximately 5mL of CSF will be collected and split equally into sterile polypropylene tubes. Following the instructions within the Laboratory Manual, CSF samples are to be frozen (within 30 minutes of collection) and shipped to the central laboratory.

CSF samples will be collected during the Screening Period and again at Week 76 for those subjects participating in the CSF Biomarker sub-study. We currently plan to assay the following biomarkers:

- Total Tau
- P-tau181 and/or P-tau217
- Neurogranin
- sTREM2
- Amyloid-beta 42
- Neurofilament light chain

# 8. COGNITIVE AND FUNCTIONAL ASSESSMENTS

# 8.1. MINI-MENTAL STATE EXAM (MMSE)

The MMSE is a set of standardized questions covering several target areas: orientation, registration, attention and calculation, short-term verbal recall, naming, repetition, 3-step command, reading, writing, and visuospatial cognitive assessment. Administration of the MMSE is estimated to take approximately 10 minutes.

# 8.2. CLINICAL DEMENTIA RATING (CDR)

Washington University's CDR^7 characterizes six domains of cognitive and functional performance applicable to AD and related dementias: memory, orientation, judgment and problem solving, community affairs, home and hobbies, and personal care. The study partner is interviewed first by a qualified rater who assesses all six domains in the absence of the study subject. The subject is then interviewed by the same rater in the absence of the study partner. A CDR global score can be calculated by accessing Washington University's online algorithm (https://biostat.wustl.edu/~adrc/cdrpgm/index.html) where 0 = no dementia, and scores of 0.5, 1, 2, or 3 = questionable, mild, moderate, or severe dementia, respectively. The sum of boxes (i.e., CDR-SB) can also be calculated by summing the six individual domain scores. This detailed quantitative general index may provide more information than the CDR-GS in patients with mild dementia.

# 8.3. ALZHEIMER'S DISEASE ASSESSMENT SCALE – COGNITIVE SUBSCALE 12 (ADASCOG12)

The ADAS-Cog is a psychometrician-administered battery comprised of several cognitive domains including memory, comprehension, praxis, orientation, and spontaneous speech. The ADAS-Cog12 (which includes Delayed Word Recall) will be administered to all subjects at various key visits throughout the study.

# 8.4. NEUROPSYCHIATRIC INVENTORY (NPI)

A study partner interview, the 12-item NPI records frequency and severity of common neuropsychiatric symptoms in dementia (Hallucinations, Delusions, Agitation/aggression, Dysphoria/depression, Anxiety, Irritability, Disinhibition, Euphoria, Apathy, Aberrant motor behavior, Sleep and nighttime behavior change, Appetite and eating change). The study partner is then asked to rate their own distress for the subject's behavioral symptoms occurring in the past 4 weeks.

# 8.5. ALZHEIMER'S DISEASE COOPERATIVE STUDY – ACTIVITIES OF DAILY LIVING (ADCS-ADL-AD)

The ADCS-ADL is a 23-item study partner questionnaire that covers both basic activities of daily living (ADL) (e.g., eating and toileting) and more complex ADL or instrumental ADL (e.g., using the telephone, managing finances, preparing a meal).

# 8.6. COLUMBIA-SUICIDE SEVERITY RATING SCALE (C-SSRS)

The C-SSRS is an assessment tool used to assess the lifetime suicidality of a subject (C-SSRS at baseline) as well as any new instances of suicidality (C-SSRS since last visit).

# 8.7. ZARIT BURDEN INTERVIEW (ZBI)

The ZBI is a 22-item scale designed to assess the stress or burden experienced by caregivers of people with dementia. The ZBI will be administered as an interview with the caregiver. The scale consists of 22 statements reflecting how people can feel when taking care of another person. The statements are phrased as questions for the caregiver to indicate how often they feel the way described in the statement. The 5 possible responses for each item are Never, Rarely, Sometimes, Quite Frequently, and Nearly Always.

# 8.8. GERIATRIC DEPRESSION SCALE (GDS)

The GDS is a 30-item yes/no question test designed to screen for depression in elderly persons. The GDS short form (15-items) version utilized in this study will be clinician administered with caregiver input. Subjects will be evaluated for symptoms of depression during the Screening Period. The GDS scale score should be clinically interpreted to evaluate the potential for a major depressive episode by a clinician who has been trained on the scale and is familiar with the diagnosis of major depression.

# 8.9. ELECTRONIC CAPTURE OF RATING SCALES

The assessments MMSE, CDR, ADAS-Cog12, GDS, NPI, ADCS-ADL, C-SSRS, and ZBI will be captured electronically by an eCOA platform that is 21 CFR Part 11 compliant. Data collected by eCOA will be transferred directly to the EDC vendor's database.

The electronic capture of the rating scales will include an audio recording for the purpose of monitoring site staff performance during scale questionnaire administration and providing constructive feedback to the raters. Subject data captured on recordings will not be analyzed as part of the trial outcomes. The Investigator or rater will read the questions out loud to study participants who will then respond. The process of questions and answers will be recorded using an audio-recording device. These highly secured recordings will not

be made public at any time and will be destroyed after the Study Drug has been either approved or disapproved for use by the FDA or other pertinent regulatory bodies.

#### 9. EARLY DISCONTINUATION

Subjects may choose to discontinue Study Drug or study participation at any time, for any reason, and without prejudice. Moreover, a subject may be withdrawn at any time at the discretion of the Investigator or Sponsor for safety, behavioral or administrative reasons. Discontinued subjects should be followed according to medical practice standards, and the outcome documented. Follow-up is required if the subject is discontinued due to an adverse event (AE). Any comments (spontaneous or elicited) or complaints made by the subject and the reason for termination and the date of stopping the drug must be recorded in the Case Report Form (CRF) and source documents.

The following must be completed and documented in the source documents and CRFs for all subjects who discontinue the study early:

- The reason for early study discontinuation. If the subject is withdrawn for more than one reason, each reason should be documented in the source documents and the most clinically relevant reason should be entered on the CRF.
- Vital signs (blood pressure, temperature and pulse), brief physical and neurologic examination, weight, clinical laboratory tests, 12-lead resting ECG (5 min supine), use of concomitant medications and adverse events should be obtained at discharge prior to release.
- Blood draw for plasma biomarkers
- ADAS-Cog12, MMSE, CDR, ADCS-ADL, NPI, ZBI and C-SSRS (as detailed in Section 7.1.7 Early Termination Visit), if not performed within the last 30 days.

#### 10. ADVERSE EVENTS/SERIOUS ADVERSE EVENTS

#### 10.1. ADVERSE EVENTS – DEFINITION

An Adverse Event (AE) is any undesirable event that occurs to a subject during a study, whether or not that event is considered related to Study Drug. Monitoring for AEs will start after informed consent has been obtained. Examples include:

- Any treatment-emergent signs and symptoms (events that are marked by a change from the subject's baseline/entry status [e.g., an increase in severity or frequency of pre-existing abnormality or disorder])
- All reactions from Study Drug, an overdose, abuse of drug, withdrawal phenomena, sensitivity or toxicity to Study Drug
- Apparently unrelated illnesses
- Injury or accidents (Note: if a medical condition is known to have caused the injury or accident, the medical condition and the accident should be reported as two separate medical events [e.g., for a fall secondary to dizziness, both "dizziness" and "fall" should be recorded separately])
- Extensions or exacerbations of symptoms, subjective subject-reported events, new clinically significant abnormalities in clinical laboratory, physiological testing or physical examination

All AEs, whether or not related to Study Drug, must be fully documented on the AE page of the CRF and in the subject's clinical chart. Adverse events reported during the screening period or AEs secondary to study-related procedures should always be captured as not having a reasonable possibility the AE was caused by the Study Drug. Unexpected, abnormal laboratory results observed during the Screening Period should be captured as Medical History and not as an AE.

In the event that a subject is withdrawn from the study because of an AE, it must be recorded on the CRF as such. The subject should be followed and treated by the Investigator until the abnormal parameter or symptom has resolved or stabilized.

The Investigator must report all directly observed AEs and all spontaneously reported AEs. The Investigator will ask the subject a non-specific question (e.g., "Have you noticed anything different since your dose of the study medication?") to assess whether any AEs have been experienced since the last assessment. AEs will be identified and documented in the Electronic Data Capture (EDC) system in appropriate medical terminology. The severity and the relationship to the Study Drug will be determined and reported in EDC (see below).

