#### 3. STUDY OBJECTIVES

The primary objective of this study is to investigate the safety and efficacy of simufilam in slowing cognitive and functional decline following 76-week, repeat-dose oral administration in mild-to-moderate AD subjects, 50-87 years of age. Secondary objectives are to assess neuropsychiatric symptoms and to replicate the CSF biomarker effects observed in the two Phase 2 studies (PTI-125-03 and PTI-125-02) after 76 weeks of simufilam treatment. A third objective is to investigate the effect of simufilam treatment on plasma biomarkers as well as anatomical correlates of disease progression (brain volume [hippocampus, ventricles and whole brain]; amyloid and tau deposition in the brain).

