#### 4. SUMMARY OF STUDY DESIGN

In this Phase 3 clinical study, approximately 1,083 subjects with mild-to-moderate AD (361 per arm) will receive placebo or 50 mg tablets of simufilam or 100 mg tablets of simufilam, twice daily, for 76 weeks. Randomization (1:1:1) will be stratified by low or high MMSE (16-20 and 21-27).

Subjects, 50-87 years of age, will be selected for screening based on a diagnosis of AD consistent with Stages 4 or 5 on the Alzheimer's continuum (National Institute on Aging – Alzheimer's Association 2018). Subjects must have MMSE  $\geq$  16 and  $\leq$  27, and a Clinical Dementia Rating Global Score (CDR-GS) of 0.5, 1 or 2. Finally, subjects must have confirmed PET or fluid biomarker evidence of AD pathophysiology prior to randomization (see Section 5.2 – Inclusion Criteria for details).

Once subjects have been satisfactorily screened for study participation, visits to the research clinic will occur on Study Day 1 and at Weeks 4, 16, 28, 40, 52, 64 and 76.

The co-primary endpoints include the 12-item Alzheimer's Disease Assessment Scale – Cognitive Subscale (ADAS-Cog12) and the Alzheimer's Disease Cooperative Study – Activities of Daily Living (ADCS-ADL), both assessed as the change from baseline to the end of the double-blind treatment period (Week 76).

Secondary endpoints include the integrated Alzheimer's Disease Rating Scale (iADRS), Neuropsychiatric Inventory (NPI), MMSE, and Clinical Dementia Rating Sum of Boxes (CDR-SB). A brief questionnaire assessing caregiver burden, the Zarit Burden Interview (ZBI), will be collected as an additional secondary endpoint.

Safety will be evaluated by adverse event monitoring, vital signs, clinical labs, and the Columbia Suicide Severity Rating Scale (C-SSRS) at every visit. Subjects will undergo MRI during screening to ensure entry criteria are met (unless recent MRI confirms entry criteria); however, 150 subjects (50 subjects per treatment group) will also undergo repeat MRI assessments at Weeks 40 and 76 to assess both long-term safety and drug impact on brain volume as noted above. Resting ECGs will be conducted at Baseline (Study Day 1) and Weeks 4, 40 and 76. A complete physical and neurological examination will be performed at screening, and brief examinations will be performed at all other visits. Weight will be measured during the Screening Period, at Baseline (Study Day 1) and at all other visits.

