- 9. Male subjects must be willing to use contraception during the study. With female partners of childbearing potential, male subjects, regardless of their fertility status, must agree to either remain abstinent or use condoms in combination with one additional highly effective method of contraception (e.g., oral or implanted contraceptives, or intrauterine devices) or an effective method of contraception (e.g., diaphragms with spermicide or cervical sponges) during the study and for 14 days after Study Drug dosing has been completed.
- 10. Fluency in a language of the research site and the utilized assessment materials.
- 11. Has adequate visual and auditory acuity (in the Investigator's judgment) that is sufficient to complete all scheduled assessments (eyeglasses and hearing aids are permitted).
- 12. If receiving background AD medications, including cholinesterase inhibitors, memantine, neuroleptics, anxiolytics, or sleep medications, the dosing regimen must be stable for at least 12 weeks prior to Study Day 1 (randomization) and should be expected to remain stable during the study (Note barbiturates, meprobamate, and high dose benzodiazepines are not allowed, while low dose benzodiazepines, zolpidem, zaleplon and suvorexant are permitted). Chronic medications for conditions other than AD (such as depression) must be prescribed at a stable dose for at least 4 weeks prior to screening. Medications that might have a potential confounding effect on cognitive testing (either prescription or non-prescription medications) should not be modified during the Screening Period (see Section 6.3 for additional details).
- 13. The subject has not been a cigarette smoker or chewed tobacco for at least 3 years (occasional pipe or cigar smoking is permitted, but vaping is not).
- 14. Availability of a person (a study partner) who has frequent and sufficient contact with the study subject (defined as ≥10 hours per week), and can:
  - a. provide accurate information regarding the study subject's cognitive and functional abilities in the opinion of the Investigator,
  - b. agree to comply with and participate at all scheduled visits and study procedures,
  - c. sign the necessary consent form,
  - d. maintain the same level of interaction with the study subject throughout the study duration.
- 15. Individuals who have participated in a clinical study with an investigational drug

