# 7.1.8. End-of-Study / Early Termination Safety Follow-up

The subject and/or study partner will receive a follow-up phone call 7-14 days after the last dose of Study Drug for adverse event monitoring. If needed, a follow-up clinic visit will be scheduled. This phone call will thus occur Week 77 to 78 for those subjects who complete all study visits, or 1 to 2 weeks after Early Termination. If the subject reports an adverse event, the subject should be followed and treated by the Investigator until the AE has resolved or stabilized (see Section 10.1 – Adverse Events).

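### Protocol 10.1 puts its only systematic adverse-event question to the participant with dementia and gives the attending study partner no part in it, so transient symptoms between visits may be missed

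*Protocol*

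**What the plan says.** Protocol section 10.1 says who is asked about AEs: "The Investigator will ask the subject a non-specific question". The purpose is "to assess whether any AEs have been experienced since the last assessment", so the recall window runs back to the previous visit. The sample question in the same sentence refers instead to the time since the dose.

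The same paragraph opens with two further routes: "The Investigator must report all directly observed AEs and all spontaneously reported AEs". It does not limit who may report. The examples of AEs in 10.1 also include new clinically significant laboratory, physiological and examination findings.

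The visit sections (7.1.4 to 7.1.7) list AE monitoring as an item and name no informant, so 10.1 is the only text that says who is asked in clinic. Section 4 gives the timetable: "visits to the research clinic will occur on Study Day 1 and at Weeks 4, 16, 28, 40, 52, 64 and 76".

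Inclusion criterion 14 (section 5.2) requires a study partner who "has frequent and sufficient contact with the study subject", set at 10 hours a week or more, and who will "agree to comply with and participate at all scheduled visits and study procedures". For the closing contact, section 7.1.8 says: "The subject and/or study partner will receive a follow-up phone call 7-14 days after the last dose of Study Drug for adverse event monitoring". Under 7.1.9 that call is not made for those who enter the open-label extension.

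Safety shares the lead objective (section 3): "The primary objective of this study is to investigate the safety and efficacy of simufilam in slowing cognitive and functional decline". SAP section 9 summarises safety descriptively, without tests unless otherwise specified. SAP 9.1.3 reports the number and proportion of participants with each event and counts a participant once per preferred term.

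**The concern.** Participants enter with a screening MMSE of 16 to 27 and a CDR global score of up to 2, which protocol 8.2 labels moderate dementia. Criterion 1 also admits people who cannot give written consent themselves. They are asked an open question about, in most cases, the past three months. A dizzy spell, a fall or a few days of nausea may be forgotten and leave nothing for a later blood test or examination to find.

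The partner is better placed to remember such events. Section 7.1.4 has the partner give study drug twice daily, and from Day 1 the partner is interviewed for the ADCS-ADL and ZBI at every clinic visit. The protocol relies on the partner for function, behaviour, dementia staging and, after the last dose, AEs. Leaving the partner out of the enquiry during treatment does not fit that pattern.

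What is at stake is the completeness of the AE tables. Severity and causality ratings (10.2, 10.3) also draw on the subject's report.

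**Working it through.** **1. Figures in the plan.** The documents state no AE rate and no capture rate, so there is no safety figure to reproduce. The arm size comes from the efficacy calculation in protocol 11.5, which does reproduce: the effect is 0.45 × 6.0 = 2.7 points, and n = 2 × (1.960 + 1.282)² × 10.0² / 2.7² ≈ 288.3, rounded up to 289 per group. Then 289 / 0.80 = 361.25, against 361 stated.

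**2. Recall windows.** Visits at Weeks 0, 4, 16, 28, 40, 52, 64 and 76 give gaps of 4, 12, 12, 12, 12, 12 and 12 weeks. Six of seven are 12 weeks.

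**3. Who is asked, and when.**

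| Contact | Named AE informant | Partner's other role |
|---|---|---|
| Clinic visits, Day 1 to Week 76 | Subject (10.1) | ADCS-ADL and ZBI at each; NPI at four; CDR at Week 76 |
| Call 7 to 14 days after last dose | Subject and/or partner (7.1.8) | None |
| Entry to the extension | Call omitted (7.1.9) | None |

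A participant who enters the extension may therefore finish the trial without any AE enquiry that names the partner.

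**4. What the other routes still catch.** Laboratory tests, vital signs, weight and a brief examination take place at every visit, and unscheduled visits for AEs are possible (7.1.10). If these routes and volunteered reports catch a fraction f, and the question independently catches s, overall capture is 1 − (1 − f)(1 − s). With assumed f = 0.5 and s = 0.6 this is 1 − 0.5 × 0.4 = 0.80. Transient symptoms are the case where f is likely to be low.

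**5. Effect on the arm comparison.** Let p₀ and p₁ be true participant-level risks (placebo, active) and c₀, c₁ the probability that an affected participant is recorded. With no false reports, the observed risks are c₀p₀ and c₁p₁. If c₀ = c₁ = c, the observed difference is c(p₁ − p₀) and the observed ratio is p₁/p₀, which does not depend on c. Illustration with assumed p₀ = 10% and p₁ = 18%:

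| Capture, placebo / active | Observed risks | Difference (points) | Ratio |
|---|---|---|---|
| 1.0 / 1.0 | 10.0% vs 18.0% | 8.0 | 1.80 |
| 0.8 / 0.8 | 8.0% vs 14.4% | 6.4 | 1.80 |
| 0.6 / 0.6 | 6.0% vs 10.8% | 4.8 | 1.80 |
| 0.4 / 0.4 | 4.0% vs 7.2% | 3.2 | 1.80 |
| 0.6 / 0.8 | 6.0% vs 14.4% | 8.4 | 2.40 |
| 0.8 / 0.6 | 8.0% vs 10.8% | 2.8 | 1.35 |

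Assumed risks of 5% and 10% behave the same way: differences of 5.0, 4.0, 3.0 and 2.0 points at c = 1.0, 0.8, 0.6 and 0.4, with a ratio of 2.00 throughout. The last two rows of the table show that unequal capture can exaggerate the comparison or hide it.

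**6. Rare events.** For an event with an assumed true risk of 0.5%, the chance that an arm of 361 records at least one case is 1 − (1 − 0.005)³⁶¹ = 84% at full capture and 1 − (1 − 0.003)³⁶¹ = 66% at c = 0.6.

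**The case against.** The best case for the plan is that 10.1 does not rest on the question alone. It requires observed and spontaneously reported events to be recorded whoever reports them. The partner is in the clinic at every visit and free to speak, and nothing bars a site from asking. Objective safety measurements are repeated throughout. The liver thresholds in 7.1.11 all start from a laboratory value, and only some branches add symptoms. All of this stands, and it is why the point is limited to transient, non-serious symptoms. What remains is that volunteering information is not the same as being asked, and the protocol's own closing call accepts the partner as an AE informant.

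It can also be objected that a capture fraction per event overstates the loss, because the SAP counts participants. With two independent occurrences and 0.5 capture of each, the participant is counted with probability 1 − 0.5² = 0.75. That is correct, and it is why the capture figures in the table are defined per participant.

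The mismatch in the sample question is minor: it is only an example, and the operative window is stated beside it.

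**Conclusion.** This is a cheap improvement to a stated method. The gap in the text is clear: the one systematic enquiry goes to the subject, mostly over 12 weeks, with no stated role for the partner. Its consequence is a risk, namely that AE incidence is understated for transient, non-serious symptoms and, with equal capture across arms, that absolute differences are understated too. The illustrative sizes rest on assumed risks and capture rates, equal capture where so stated, and no false reports. The real size cannot be computed from the documents.

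A reader might infer three stronger things that the documents do not support:

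- That events are in fact under-recorded. No capture rate is given, and nothing shows how sites actually asked.
- That arm differences shrink toward zero. This holds only for the absolute difference under equal capture. The risk ratio is then unchanged, and with unequal capture the direction is open.
- That the trial loses power to detect harm. SAP section 9 plans a descriptive safety summary, so a power figure would describe a test that is not planned.

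**What to change.** In protocol 10.1, direct the question to the subject and the study partner, and apply this at each visit under 7.1.4 to 7.1.7. Add a field on the AE page for who reported the event. Reword the sample question so that it covers the period since the last assessment.

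The cost is a sentence of protocol text and one form field. The partner is already present and interviewed, so no extra visit or procedure is needed. The downside is slightly higher recorded AE rates in all arms.

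SAP 2.1 reports that the study was stopped early, so an amendment cannot recover events already missed. For this trial the study report should state who was asked about AEs and note the limitation. The revised wording would serve any later protocol that reuses this section.
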